CK-MB	Cooperative Studies Scientific Evaluation Committee
VAMC	Creatine kinase MB
NODES	VA Medical Centers
DMC	Network of Dedicated Enrollment Sites
VA CIRB	Data Monitoring Committee
IRB	VA Central Institution Review Board
HIPAA	Institution Review Board
ITTRS	Health Insurance Portability and Accountability Act
FDA	Interactive Touchtone Telephone Randomization System
RCRI	Food and Drug Administration
GCP	Revised Cardiac Risk Index
GCPMG	Good Clinical Practice
	Good Clinical Practice Monitoring Group

GCPSRG	Good Clinical Practice Standards and Resource Group
BMI	Body Mass Index
HRC	Human Rights Committee
AE	Adverse Events
SAE	Serious Adverse Events
R&DC	Research & Development Committee
ICH	The International Conference on Harmonization
ICH-E2A	ICH Clinical Safety Data Management
SOP	Standard Operation Procedure
MedDRA	Medical Dictionary for Regulatory Affairs
CSRD	Clinical Science Research and Development
SAP	Statistical Analysis Plan
PHI	Personal Health Information
CFR	Code of Federal Regulations
FIPS	Federal Information Processing Standard
SSN	Social Security Number
SMART	Site Monitoring, Auditing and Resource Team
LSI	Local Site Investigator
ITT	Intent-to-Treat
CI	Confidence Interval
OR	Odds Ratio
SBP	Systolic Blood Pressure
DBP	Diastolic Blood Pressure
RCT	Randomized Controlled Trial
R&D	Research & Development
SC	Study Coordinator
SI	Site Investigator
VA	Veterans Affairs

1. SUMMARY

The overall goal of the proposed study is to determine whether a liberal transfusion strategy (transfusion trigger at Hb<10gm/dl) in patients at high risk for postoperative cardiac events who undergo open vascular and general surgery operations is associated with decreased risk of adverse postoperative outcomes compared to a restrictive transfusion strategy (transfusion trigger at Hg < 7 gm/dl). This study will compare all-cause mortality and other complications between the liberal (transfusion trigger at Hb<10gm/dl) and restrictive (transfusion trigger at Hb<7gm/dl) transfusion policies for high cardiac risk patients who undergo surgical procedures. The study will randomize 1520 patients from 15 participating sites over a four-year recruitment period. The primary end point of the study is a composite event of 90-day all-cause mortality, myocardial infarction (MI), coronary revascularization, stroke, and acute renal failure after randomization. The study hypothesis is that the liberal transfusion policy group will have a lower composite event rate than the restrictive transfusion policy group. Secondary objectives of this study include: 1) to examine the effect of transfusion strategy on post-randomization infectious complications, 2) to examine the effect of transfusion strategy on post-randomization cardiac complications other than MI, 3) to examine the effect of transfusion strategy on all-cause mortality up to one year after randomization, 4) to examine the effect of transfusion strategy on a composite endpoint of all-cause post-randomization mortality, MI, coronary revascularization, acute renal failure, and stroke up to 30 days after randomization, and 5) to examine the effect of transfusion strategy on length of hospital stay.

This statistical analysis plan (SAP) is drafted after review of the current CSP-599 study protocol and case report forms (CRFs). Detailed information is given to aid in the production of the statistical output and the statistical section of the final study report, and potential manuscripts for publication. This document provides background of the study based on the protocol and describes the populations that will be analyzed. All subject characteristics and the efficacy and safety parameters that will be evaluated, along with the specific statistical methods, are described.

2. INTRODUCTION

2.1. Background

Blood is an indispensable product in modern medical practice.¹ Red blood cells (RBC) replace intravascular volume, improve oxygen delivery to tissues in situations of hemorrhage, and anemia² and consist one of the few treatments that adequately restore tissue oxygenation and maintain life when oxygen demand exceeds supply.^{3,4} Currently there is no physiologic test to assist with clinical decision-making. The lack of sophisticated physiologically driven transfusion algorithms has led to the development of the “transfusion trigger” concept, which dictates that a specific level of hemoglobin (Hb) should be used to guide transfusion decisions. Historically, the widely accepted clinical standard has been to transfuse patients when the Hb level drops below 10gm/dl or the hematocrit falls below 30% and served as RBC transfusion guide for decades^{4,5}.

Blood is a finite resource whose collection depends on the availability of donors and its processing is costly and time consuming.^{1,6,7,8,9,10-12} Therefore, clinicians sought to determine the safety of more restrictive blood transfusion strategies. Hebert et al.¹³ studied the impact of transfusion strategy in the ICU setting. The authors demonstrated that a restrictive transfusion strategy that accepted Hb as low as 7gm/dl did not have an adverse impact on survival, although a post-hoc analysis¹⁴ of this trial that included a subset of patients with known ischemic heart disease demonstrated a trend for increased mortality in the restrictive transfusion group.

Since then other randomized trials have examined the impact of transfusion strategy on specific patient populations using various combinations of restrictive and liberal thresholds, including trials in patients undergoing cardiac surgery¹⁵, in patients undergoing hip replacement,¹⁶ in patients with septic shock¹⁷, and in patients with acute upper gastrointestinal bleeding¹⁸. These trials suggested a restrictive transfusion strategy was well tolerated in these specific populations and one trial¹⁸ even demonstrated the restrictive transfusion strategy was superior.

Published guidelines^{2,19-21} and health policy statements²² place a lot of emphasis on the need for restrictive transfusion thresholds in a variety of clinical settings; at the same time, the guidelines acknowledge²¹ that a substantial area of uncertainty remains and concerns the patients with underlying cardiovascular disease, a population that is more likely than any other

to be extremely sensitive to transfusion thresholds. Data on these high cardiac risk patients remain scarce, coming mainly from small trials and secondary analyses²³⁻²⁴. In the recently published TITRe2 trial²⁵ with 2007 patients undergoing cardiac surgery randomized to a liberal (trigger Hb < 9 gm/dl) or a restrictive (trigger Hb < 7.5 mg/dl) transfusion arm, the primary endpoint (a composite of a serious infection or an ischemic event at 90 days after randomization) was not different between the two groups. However, mortality at 90 days was more likely in the restrictive group.

As the world is progressively moving towards more restrictive transfusion standards, the unanswered question of transfusion thresholds in high cardiac risk patients has created a knowledge gap that requires urgent attention. Given the magnitude of ischemic heart disease (IHD) as health care problem²⁶, this uncertainty creates a critical patient safety issue.

In order to address this knowledge gap, we propose a randomized trial to compare two transfusion strategies in high cardiac risk patients undergoing vascular and general surgery operations. The study cohort will include patients with known history of IHD and IHD equivalent diseases (ischemic stroke, or peripheral artery disease [PAD]). PAD is a well-known marker of IHD and myocardial infarction represents the leading cause of mortality after PAD-related operations.²⁷ Furthermore, patients in the proposed study will not have their coronary artery lesions routinely repaired during or prior to the index operation, and therefore their risk of cardiac events postoperatively will remain at least as high as it was preoperatively.

2.2. Goal of the Study

The goal of the proposed study is to determine whether a liberal transfusion strategy (transfusion trigger at Hb < 10 gm/dl) in Veterans at high cardiac risk who undergo major open vascular and general surgery operations is associated with decreased risk of adverse postoperative outcomes compared to a restrictive transfusion strategy (transfusion trigger at Hb < 7 gm/dl).

3. STUDY OBJECTIVE AND ENDPOINTS

3.1. Study Objectives and Hypotheses

Primary Objective:

Objective 1: To examine the effect of transfusion strategies on a composite endpoint of all-cause post-randomization mortality, myocardial infarction (MI), coronary revascularization, acute renal failure, or post-randomization stroke in Veterans at high cardiac risk undergoing open surgical interventions.

Primary Hypothesis:

Hypothesis 1: A significantly smaller proportion of participants receiving blood under a liberal transfusion strategy will experience the composite compared to participants under restrictive transfusion strategy at 90 days after randomization.

Secondary Objectives:

Objective 1: To examine the effect of transfusion strategies on post-randomization infectious complications.

Hypothesis 1: A smaller proportion of participants receiving blood under a liberal transfusion strategy will experience post-randomization infectious complications compared to participants under restrictive transfusion strategy at 90 days after randomization.

Objective 2: To examine the effect of transfusion strategies on post-randomization cardiac complications other than MI.

Hypothesis 2: A smaller proportion of participants receiving blood under a liberal transfusion strategy will experience post-randomization cardiac complications other than MI compared to participants under restrictive transfusion strategy at 90 days after randomization.

Objective 3: To examine the effect of transfusion strategies on all-cause mortality during the one-year post-randomization follow-up.

Hypothesis 3: A smaller proportion of participants receiving blood under a liberal transfusion strategy will die from any cause compared to participants under restrictive transfusion strategy during one year follow-up after randomization.

Objective 4: To examine the effect of transfusion strategies on a composite endpoint of all-cause post-randomization mortality, MI, coronary revascularization, acute renal failure, or post-randomization stroke at 30 days after randomization.

Hypothesis 4: A smaller proportion of participants receiving blood under a liberal transfusion strategy will experience the composite endpoint compared to participants under restrictive transfusion strategy at 30 days after randomization.

Objective 5: To examine the effect of transfusion strategies on the length of hospital stay

Hypothesis 5: Liberal transfusion strategy will lead to a shorter length of hospital stay.

Tertiary Objective:

Objective: To examine the effect of transfusion strategies on the components of the primary endpoint.

Hypotheses: A smaller proportion of participants receiving blood under a liberal transfusion strategy will experience post-randomization death from any cause, MI, coronary revascularization, acute renal failure, or post-randomization stroke, compared to participants under restrictive transfusion strategy at 90 days after randomization.

3.2. Study Outcome Variables

3.2.1. Primary Outcome Variable

The primary outcome is defined as a composite endpoint of all-cause post-randomization mortality, myocardial infarction (MI), coronary revascularization, acute renal failure, or post-randomization ischemic stroke up to 90 days after randomization.

MI will be defined using the Third Universal Definition of Myocardial Infarction.²⁸

Acute renal failure will be defined as Acute Kidney Injury stage III according to RIFLE criteria: Serum creatinine rise greater than 3 times that of baseline creatinine; or if baseline serum creatinine is greater than 4 mg/dl, then rise more than 0.5 mg/dl compared to baseline; or urine output less than 0.3ml/Kg/hr for 24 hours; or anuria for 12 hours. Baseline creatinine will be considered the creatinine upon admission prior to the index operation. The above urine output criteria will be only used for patients who are in the ICU and have precise monitoring of their urinary output. For patients on the surgical floor only serum creatinine changes will be used for assessment of this endpoint.

Coronary revascularization will be defined as a coronary artery bypass graft, or percutaneous coronary intervention (either angioplasty or stenting).

Stroke will be defined as new unilateral neurological deficit that lasts for more than 24 hours and is confirmed by a brain imaging modality (either computed tomography or magnetic resonance imaging study) demonstrating new brain infarct.

3.2.2. Secondary Outcome Variables

There are five secondary outcome measures based on their use in previous studies.

Outcome 1: A composite endpoint of post-randomization infectious complications at 90 days post-randomization: Infectious complications will include wound infections, pneumonia, and sepsis.

Wound infection will be defined according to the Centers for Disease Control and Prevention (CDC) guidelines as a) positive wound culture, or b) drainage of pus from a wound, or c) suspicion of wound infection that was drained operatively.

Pneumonia will be defined according to the CDC definition as chest radiograph or imaging with new or progressive infiltrate, consolidation, cavitation, or pleural effusion and any of the following: new onset of purulent sputum or change in character of sputum, or organism isolated from blood culture, trans-tracheal aspirate, bronchial brushings, or biopsy.

Sepsis will be defined as a combination of two of the following systemic inflammatory response syndrome (SIRS) criteria, plus suspected or present source of infection. SIRS criteria will include the following: temperature greater than 38C, heart rate greater than 90 beats/min, WBC > 12,000 or < 4,000, or > 10% bands.

Outcome 2: A composite endpoint of cardiac complications (other than MI) at 90 days post-randomization: Cardiac complications will include new cardiac arrhythmias that necessitate new treatment, congestive heart failure (CHF) exacerbation, and cardiac arrest.

The diagnosis of cardiac arrhythmias will be based on EKG findings. Only arrhythmias that result in initiation of new treatment regimen (to include medications, implantable devices, or surgical intervention) during hospitalization will be recorded.

CHF will require at least one of the following symptoms or signs new or worsening: dyspnea at rest, orthopnea, or paroxysmal nocturnal dyspnea and radiological evidence of heart failure or worsening heart failure and increase/initiation of established treatment.

Cardiac arrest will be defined as the cessation of cardiac pump function activity that results in loss of consciousness and absence of circulating blood flow as evidenced by absent

carotid pulse. Only episodes of cardiac arrest that are reversed will be collected under this endpoint. If they are not reversed the event will be categorized as death.

Outcome 3: All-cause mortality at 1 year after randomization.

Outcome 4: A composite endpoint of all-cause mortality, MI, coronary revascularization, acute renal failure, or post-randomization stroke at 30 days after randomization.

Outcome 5: Length of hospital stay after randomization.

3.2.3. Tertiary Outcome Variables

Individual rates of the outcomes that consist of individual components of the primary endpoint

3.2.4. Safety Outcome Variables

Safety measures include serious adverse events and laboratory assessments.

4. STUDY METHODS

4.1. General Study Design

The study is a parallel, single-blind, controlled, superiority trial in which participants will be randomized to a restrictive or a liberal transfusion group. This study will randomize 1520 Veterans at 15 VA Medical Centers. The total recruitment period will be approximately 4 years which will be followed by a 3 month active and 9 month passive follow-up period. The duration of the study will be approximately 5 years. Consent for the study will be obtained prior to the index surgical intervention at the clinic visit or, in case of inpatients, at the hospital ward pre- or postoperatively. Randomization will be performed via a central telephone randomization system once the participant has a confirmed post-operative Hb < 10gm/dl. Active follow up will be up to three months after randomization. Passive follow up will be from 3 months to one year after randomization. The study flow is shown in Appendix 1. There will be no blinding at the treating physician level; however the participants and the Endpoint Committee will be unaware of group allocation.

Follow up forms will be filled out during two postoperative clinic visits that will be after the 30th and 90th post-randomization days. Participants who cannot make the clinic visits will be assessed by phone call follow-up, during which they will be asked specific questions to ascertain whether signs or symptoms related to any of the endpoints have developed. In

addition, the electronic medical record, will be assessed to collect relevant information. If a participant gets re-admitted at any time after discharge and within 90 days after randomization, the electronic medical record will be examined for the presence of any of the diagnoses that consist part of either the primary or any other endpoints. If the participant has been admitted to a non-VA facility, a full copy of hospital records from that admission will be obtained and assessed for the presence of any of the outcomes. History and physical, consultation notes and progress notes will all be reviewed. Furthermore, particular attention will be paid to laboratory reports for troponin, creatinine, CK-MB, and WBC levels, reports of cardiac echograms, radiology reports, and results of cultures (blood, wound, sputum). Participant agreement for release of information to the study personnel for all postoperative hospital visits that occur within 90 days after randomization will be obtained as part of the original consent form.

Assessment of one year mortality will be performed as part of a passive follow up performed by the Chairman's office via examination of the electronic medical record, follow up phone calls, and search of national databases documenting mortality.

4.2. Inclusion-Exclusion Criteria and General Study Population

All Veterans who are scheduled to undergo vascular or general surgery at a VAMC will be invited to participate in this trial. The inclusion and exclusion criteria are outlined below.

A. Inclusion Criteria

- 1) Male and female Veterans older than 18 years of age who have postoperative Hb < 10gm/dl within 15 days after the index operation
- 2) Patients undergo an operation in either one of the three following categories
 - a. Veterans who undergo PAD – related operations including but not limited to the following: aortobifemoral or aortobiiliac bypass, open abdominal aortic aneurysm repair with simultaneous repair of aortoiliac occlusive disease, visceral bypass, iliofemoral bypass, femoral bypass or endarterectomy, infrainguinal bypass; thromboembolectomy; supra-aortic trunk bypass or endarterectomy, carotid endarterectomy, and major lower extremity amputations (transfemoral, through the knee, or transtibial)

- b. Veterans with past medical history of ischemic stroke/TIA of likely carotid origin, or history of IHD (defined as known prior MI, EKG findings consistent with prior MI, prior percutaneous coronary intervention, prior coronary artery bypass surgery, history of angina for which the patient is currently receiving treatment, or stress test indicating myocardial ischemia), or history of PAD (defined as prior intervention for PAD or ABIs < 0.9) who undergo the following General Surgery operations: Open cholecystectomy or other open complex biliary reconstruction (such as open common bile duct exploration for stones, reconstruction as part of oncologic operations such as palliative pancreatic cancer procedures), open or laparoscopic small bowel resection, pancreatectomy, colon resection, colostomies (reversals and takedowns), intestinal anastomosis takedown and revision, rectal resection, splenectomy, transhiatal esophagectomy, liver resection, gastric operations (resections or repairs), gastric bypasses, adrenalectomy, major diaphragmatic hiatal hernia repair, Nissen fundoplications, and ventral hernia repair
- c. Veterans with past medical history of ischemic stroke/TIA of likely carotid origin, or history of IHD, or history of PAD (defined as prior intervention for PAD or ABIs < 0.9) who undergo the following Vascular Surgery operations: Open aneurysm repair (including but not limited to carotid, subclavian, abdominal aortic, iliac, femoral, or popliteal aneurysms); and complex endovascular aneurysm repair (defined as fenestrated endograft, or endograft with need for iliac conduit, or endovascular aneurysm repair with simultaneous femoral artery reconstruction or bypass). Subclavian/vertebral bypasses and transpositions are eligible with a history of PAD/IHD/ischemic stroke.

B. Exclusion Criteria

- 1) Veteran unable to consent
- 2) Veteran unwilling to follow protocol (such as Jehovah's witnesses)

- 3) Veteran with known history of hereditary anemias such as Thalassemia or Sickle cell disease
- 4) Veteran with known history of hereditary bleeding disorders, such as factor VIII or factor IX deficiency
- 5) Veteran with prior history of adverse reaction to blood administration, such as fever, rash, or hemolysis
- 6) Veteran does not speak or understand English
- 7) Veteran hemodynamically unstable (systolic blood pressure <90 and heart rate >100 that persists for at least 30 minutes) or in cardiogenic shock for \geq 48 hours after the index procedure
- 8) Veterans participating in another interventional trial
- 9) Pregnancy in female Veterans
- 10) Veteran is a prisoner or in custody of law enforcement
- 11) Prior randomization in the CSP#599
- 12) Patients who are known to have tested positive for COVID-19 and have not recovered prior to consent will not be consented. Any participant who is known to have a positive COVID-19 test during the screening process and has not recovered will be excluded prior to randomization.

Recovery from COVID-19 is defined as a patient who is asymptomatic (per local preoperative clearance policies) and at least 10 days post a positive test.

4.3. Randomization and Blinding

The clinical site coordinator will track the participants' postoperative Hb levels and identify participants whose Hb level is below 10 gm/dl and therefore eligible for randomization. iStat hemoglobin values may not be used as the basis for randomization/transfusion decisions. The CSPCC staff will prepare randomization schedules for each clinical site participating in the study. The study randomization to either liberal or restrictive transfusion policy will be done by an Interactive Touchtone Telephone Randomization System (ITTRS). A stratified block randomization scheme with block sizes of 2 and 4 will be used to randomize participants in the two transfusion groups. The stratifying factors are clinical site and revised cardiac risk index

(RCRI) class. The participants and the Endpoint Committee will be unaware of treatment group allocation.

4.4. Study Assessments Used in the Analysis

4.4.1. Baseline Assessment

Participants' demographics, medical history, physical exam, and medication use are collected. Baseline assessments will be collected the time between identification of an eligible participant and either randomization or 15 days after surgery (or until discharge, whatever comes first) including revised cardiac risk index (RCRI), patient history, hemoglobin level, ECG diagnosis, troponin, serum creatinine, albumin, and patient clinical status. Data collected during this period is used primarily for monitoring recruitment and randomization status. We will maintain the information of all identified potential participants. This will be accomplished by completing the screening form for every participant presenting to the clinical site for eligible operations including those who are excluded from the study for any reason. Following is a list of assessments that we plan on collecting:

Screening Record: To compare patient screened (but not randomized) to patient randomized in this study, a comprehensive screening assessment will be completed for all potentially eligible participants scheduled to receive a vascular/general surgery procedure at a participating center by the Study Coordinator.

Demographic and Contact Information: Following randomization, the clinical site coordinator will collect the demographic and participant information. The contact information will be used to assist with the collection of 30-day, 90-day and one year follow-up data. The demographic information will include participant's age, gender, race, marital status, etc.

Clinical Data: At the time of randomization, the site coordinator will also collect clinical data using information from the medical record and consultation with the surgeon as needed. These will include height, weight, most recent available preoperative serum Hb, albumin, blood pressure, and history of comorbidities, including coronary artery disease, end-stage renal disease, chronic obstructive pulmonary disease, hyperlipidemia, diabetes mellitus, and hypertension. To assure that MI or acute renal failure have not occurred prior to the time of randomization, the patient's chart will be reviewed for Troponin, ECG and serum Creatinine. If

these values are available in the 24 hours prior to randomization, they will not be collected again. If unavailable within this period, ECG, serum creatinine, and troponin data will be collected within 24 hours from the time of randomization.

We will also collect information on prior history of MI, coronary artery bypass, and stent placement. Furthermore, intraoperative assessments will be collected during the surgical procedure, such as type of operation, amount of intraoperative blood loss, intraoperative transfusion, amount and type of fluids administered, and length of the operation.

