4.5. Sample Size Consideration

The sample size estimation and power analysis are based on the hypothesis testing of the primary composite endpoint of all-cause post-randomization mortality, myocardial infarction (MI), coronary revascularization, acute renal failure, or post-randomization stroke up to 90 days after randomization. The primary hypothesis of the study is that in VA patients with high cardiac risk undergoing a surgical procedure, a significantly smaller proportion of participants receiving blood under a liberal transfusion strategy will experience the composite endpoint compared to participants under restrictive transfusion strategy at 90 days after randomization. The primary analysis will be done as an "intent-to-treat" analysis. Our database review revealed that 29.8% out of 25,343 patients in the VA population who were at high cardiac risk and had nadir postoperative Hb range between 6-9 gm/dl developed the composite endpoint of death, MI, acute renal failure, or coronary revascularization within 90 days from the index operation. Based on the analysis, a baseline event rate of 30% for the composite endpoint is expected in the restrictive group. We also assume a 25% reduction or 22.5% event rate in the liberal group. To detect the expected 7.5 percentage point difference or 25% reduction, a sample size of 1444 will be required at 90% power, 5% type-I error rate and with a two-sided test (Appendix 3). Assuming 5% dropout rate, then 1520 participants (or 760/group) will be needed to achieve the desired testing power.

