7.1. Primary Endpoint Analysis

The primary study endpoint will be a composite outcome of all-cause mortality, MI, coronary revascularization, acute renal failure, or post-randomization stroke within 90 days from randomization. A clinical events committee will adjudicate all component events for the primary endpoint. The number and percentage of participants with the composite endpoint at the 90-day visit after the randomization will be summarized and compared according to assigned transfusion strategy (analysis by intent to treat) using Pearson χ^2 test. Another analysis will compare primary endpoint between the two transfusion strategies stratified by clinical sites using the Cochran-Mantel-Haenszel test (Table 16a-e). The test for differences between transfusion strategies in the primary outcome will be conducted at an overall α -level of 0.05. Additional analysis will be conducted using logistic models to adjust for other clinical factors, such as age, RCRI, and nadir Hb. The interactions of the intervention with age, RCRI and nadir Hb will also be considered.

Odds ratio and 95% confidence interval (CI) will be presented using SAS PROC GENMOD or PROC LOGISTIC. Assumptions of the model including linearity in the logit of the composite event risk for continuous variables will be checked. We will assess goodness-of-fit using the statistic -2 log likelihood, which has a chi-square distribution under the null hypothesis that all the explanatory variables in the model are not associated with the outcome

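### The primary test is unadjusted, and plausible baseline predictors that the trial already collects enter no prespecified efficacy model: a missed efficiency, not a power deficit

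*SAP*

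**What the plan says.** **Primary comparison.** In SAP 7.1 the 90-day composite is to be "summarized and compared according to assigned transfusion strategy (analysis by intent to treat) using Pearson" (the chi-square test). Protocol XVI.E.2 and Protocol Table 4 name the same test. SAP 4.3 stratifies randomization by site and RCRI class; the Pearson test uses neither.

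**Analyses beside it.** SAP 7.1 adds a Cochran-Mantel-Haenszel test stratified by site only. It also adds a model: "Additional analysis will be conducted using logistic models to adjust for other clinical factors, such as age, RCRI, and nadir Hb". The Protocol's model has site and the interactions of arm with age, RCRI and nadir Hb as well. Further covariates may come in only when a model fits poorly, and they are not named.

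**What is collected.** SAP 4.4.1 lists albumin, comorbidities including end-stage renal disease, and intraoperative data such as "type of operation, amount of intraoperative blood loss, intraoperative transfusion". Of the baseline period it remarks: "Data collected during this period is used primarily for monitoring recruitment and randomization status". Pre-operative creatinine and albumin are summarized by arm (SAP 6.4, Table 11), as are end-stage renal disease and heart failure history (Table 12).

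**What the shells contain.** The adjusted efficacy shells (Tables 17, 19, 21 and 23 to 28) list arm, age, RCRI and nadir Hb. The exceptions are age of transfused blood in Tables 24 to 26 and one transfusion-by-age row in Table 23. None has a row for creatinine, albumin, operation type or blood loss. Operation type is in none of the by-arm baseline tables (Tables 10 to 15).

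**Design figures (SAP 4.5).** The planned rates are 30% under the restrictive strategy and 22.5% under the liberal one, a relative fall of one quarter. On these rates the SAP states that "a sample size of 1444 will be required at 90% power, 5% type-I error rate and with a two-sided test". An allowance of 5% for dropout brings the total to 1,520, or 760 per arm.

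**The concern.** With a binary endpoint at about 26% overall, averaging a logistic model over prognostic baseline variables estimates the same risk difference as the raw comparison, usually with a smaller standard error. It also takes account of any chance imbalance in those variables. In Protocol Table 2 the composite in the 6-9 gm/dl group is made up mainly of death (15.3%), MI (11.0%) and acute renal failure (11.1%). It is plausible that renal function, albumin, type of operation and blood loss help predict these.

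The adjusted model already planned does not fill the gap safely. Nadir Hb is not tied to the time before randomization: the SAP's abbreviation list describes it as a postoperative nadir. The Protocol expects it to differ by arm, at 6-9 gm/dl under the restrictive strategy (XVI.A), with 9-10 gm/dl representing the liberal arm (II.c). If values after randomization count, the model conditions on a consequence of treatment.

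Operation type is a separate matter. Eligibility rests on three operation categories, yet no planned table shows whether the arms are balanced on them. That gap depends on no assumption about prognostic strength.

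At stake are a somewhat narrower interval and a few points of power. The interval matters even if the null hypothesis is not rejected, because Protocol XVI.E then relies on a 95% confidence interval for the difference.

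**Working it through.** **1. Reproduce the plan's sample size.** Inputs from SAP 4.5: p1 = 0.30, p2 = 0.225, two-sided alpha 0.05, power 0.90, so the mean rate is 0.2625. Pooled-variance formula without continuity correction:

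n per arm = [1.960 × √(2 × 0.2625 × 0.7375) + 1.282 × √(0.30 × 0.70 + 0.225 × 0.775)]² / 0.075²

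= [1.2196 + 0.7945]² / 0.005625 = 4.0567 / 0.005625 = 721.2, rounded up to 722.

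The total is 2 × 722 = 1,444, and 1,444 / 0.95 = 1,520. Both match the plan. The unadjusted test has 90.0% power at 1,444.

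**2. Effect of adjustment.** If baseline covariates explain a share R² of the outcome variance, the variance of the risk difference is multiplied by about 1 − R². The interval width is then multiplied by √(1 − R²), and the effective sample size becomes 1,444 / (1 − R²). The documents give no R², so the range is an assumption. Example at R² = 0.05: the effective N is 1,520, or 760 per arm, and (0.075 × √760 − 1.2196) / 0.6200 = 1.368, which gives power of 91.4%.

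| Assumed R² | Effective N | CI width × | Power, 30% vs 22.5% | Evaluable N for 90% power |
|---|---|---|---|---|
| 0 | 1,444 | 1.000 | 90.0% | 1,444 |
| 0.01 | 1,459 | 0.995 | 90.3% | 1,430 |
| 0.05 | 1,520 | 0.975 | 91.4% | 1,372 |
| 0.10 | 1,604 | 0.949 | 92.8% | 1,300 |
| 0.20 | 1,805 | 0.894 | 95.2% | 1,156 |

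If the true rates were 30% and 24%, another row of the plan's power table, power at 1,444 would be 72.9% unadjusted. It would be 75.1, 77.3 and 81.9% at R² of 0.05, 0.10 and 0.20.

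**3. What the documents' own figures suggest about R².** They quantify only two predictors of the composite.

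- RCRI: the odds ratios of 1.8, 2.07 and 2.38 for classes II to IV against class I (Protocol II.b), at an overall rate of 26.25%, give R² of 0.018, 0.021 and 0.009. The assumed class mixes are 25/25/25/25, 40/30/20/10 and 10/30/30/30%.
- Nadir Hb: the rates are 29.5% and 15.0% (Protocol Table 2). The share in the lower group is 25,343 / 38,153 = 0.664, taking all other patients as 9-10 gm/dl, so the mean rate is 0.246. Then R² = 0.664 × 0.336 × 0.145² / (0.246 × 0.754) = 0.025.

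At R² of 0.01 to 0.025, adjustment adds 0.3 to 0.7 power points. A gain of roughly 3 to 5 points needs R² of 0.10 to 0.20.

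**4. Check by simulation.** 4,000 trials per scenario, N = 1,444, one normal prognostic score, linear adjustment with a robust standard error. The Monte Carlo error of a power near 90% is √(0.9 × 0.1 / 4,000) = 0.5 points.

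| R² (AUC of score) | Unadjusted | Adjusted |
|---|---|---|
| 0.05 (0.63) | 89.9% | 91.1% |
| 0.10 (0.70) | 90.4% | 92.4% |
| 0.16 (0.74) | 89.8% | 93.8% |
| 0.22 (0.78) | 90.0% | 94.5% |

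A second simulation used eight covariates and a standardized risk difference. At an AUC of 0.70 it gave a variance ratio of 0.91 and 92.7% power against 90.2%, which agrees. Its type I error over AUCs of 0.65 to 0.74 lay between 4.4 and 5.4% (Monte Carlo error 0.3).

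**The case against.** The best defence is that nothing here is wrong. An unadjusted intent-to-treat chi-square is valid, its type I error already allows for chance imbalance, and the sample size was set for that test. Randomization is stratified by site and RCRI class, and a site-stratified test is planned. All of this stands, and it is why the point concerns efficiency only.

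The size of the gain is also open to challenge. The two predictors that the documents quantify are weak. The calculations compare adjustment with none, so they do not isolate what creatinine, albumin, operation type and blood loss would add beyond age and RCRI. This stands too, and the range must start near zero. On the other side, the low benchmarks are for single predictors and do not cap a combined model.

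A third reply is that the covariate list is open-ended and that poor fit allows more variables. This carries less weight, because it leaves unnamed covariates to be chosen after the data are seen. Nor does the title of Table 17, where the word baseline precedes age, RCRI and nadir Hb, settle when nadir Hb is taken.

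A reader might infer from the SAP 4.4.1 sentence that baseline data are confined to recruitment monitoring. The documents do not support that. The sentence describes a collection period, and its parent section is headed as assessments used in the analysis. Admission creatinine is the reference for acute renal failure (SAP 3.2.1), and intraoperative transfusion helps define the No-Recent-Transfusion population (SAP 5.4).

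**Conclusion.** The point holds as a missed efficiency. The primary test uses no baseline information, and four plausible and already collected sources of it are in no prespecified efficacy model. The one adjusted model planned may contain a covariate that treatment affects.

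The gain is about 0.3 to 5 power points, with an interval about 0.5 to 11% narrower, over an assumed R² of 0.01 to 0.20. The result rests on that R², on the approximation that variance scales with 1 − R², and on the plan's 30% and 22.5% rates.

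Two stronger readings are tempting. One is that the trial is underpowered; it is not, since 1,444 evaluable participants give 90% power without adjustment. The other is that these variables are strong predictors whose omission costs a known number of participants; the documents give no prognostic strength for any of them.

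**What to change.** Before unblinding, prespecify in SAP 7.1 a covariate-standardized risk difference with 95% CI in the ITT population:

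- Fit a logistic model with arm, site, RCRI class, age, pre-operative creatinine (log) or end-stage renal disease, albumin, operation category (PAD-related, other vascular, general) and intraoperative blood loss.
- Average the predictions over all ITT participants under each arm, and use a model-robust standard error.
- Use only values obtained before randomization. The creatinine drawn around randomization does not qualify automatically, because SAP 4.4.1 allows it within 24 hours of randomization. Leave out post-randomization nadir Hb.
- State a simple rule for missing baseline values, such as mean imputation with a missingness indicator.

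Name this the key supportive analysis beside Pearson. The decision test and the interim rules then stay as they are. If the sponsor prefers to make it primary, Protocol XVI.E.2, Protocol Table 4 and the Z-statistic for the three interim looks (SAP 5.5.2) must be aligned with it.

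Add operation category by arm to Table 11.

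The model is affordable. The plan's rates imply 722 × 0.30 + 722 × 0.225 = 379 events. The 16 sites in the shells, with the terms above, need about 25 parameters apart from the intercept (arm 1, site 15, RCRI 3, operation 2, four single terms), or about 15 events each.

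The cost is SAP wording, a fixed covariate list, a missing-baseline rule, one more model and one table row. No new data are required.
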